### Schedule of procedures

The schedule of procedures is outlined below:

Procedure	Screening Visit	Baseline/Day 0	Day 1	Day 2	Day 3	Day 4
Informed Consent	X					
Lifestyle and Demographics Questionnaire; Anthropometrics; Dietary Screening Questionnaire, Eligibility Evaluation		X				
Anthropometric: Weight only (Non-Metabolic)			X	X	X	X
Randomization (to use PortionSize™ or MyFitnessPal first)		X				
PortionSize™ or MyFitnessPal app training and ~1 day run-in		X				
Use of app during free-living conditions			X	X	X	
Usability Surveys (MyFitnessPal & PortionSize™ specific CSUQ)						X*
PortionSize and MyFitnessPal-specific Modified Dietary Health Questionnaire (DHQIII  )						X*
PortionSize and MyFitnessPal-specific						X*
User Preference Survey						X**

\* *MyFitnessPal or PortionSize™ specific survey will occur on Day 4 in the respective period that app was utilized*

\*\**Day 4 in Period 2 will include a User Preference survey to rate the two apps*

### Power calculation

We expect no more than ~8% drop-out and will recruit at least 45 participants; hence, power analyses were conducted with a sample size of at least 42.

Estimated food intake values from the PortionSize™ and MyFitnessPal apps will be compared to directly weighed values, which serve as the criterion measure. Equivalence tests that follow the Two One-sided T-test (TOST) method will be used

(error reflects the difference between weighed intake and estimates from either PortionSize or MyFitnessPal). Based on a new power analysis and variance estimates from a recently completed pilot study, equivalence is set as within  $\pm$  17.9% of the directly weighed value. The power assumed: 42 participants, energy (kcal) intake as the outcome variable, alpha = 0.05, power  $>0.80$  as acceptable, and mean weighed intake = 2,360 kcal with an SD (difference) = 917 kcal. We will also test for equivalence at the original bound of  $\pm$  9%, as well as a new bound of  $\pm$  14%, though we recognize that these tests will likely be underpowered. Finally, with at least 42 participants completing the PortionSize and MyFitnessPal condition, we have 0.80 power to detect an R^2 of 0.17, which is acceptable as studies with Bland-Altman analysis find that poor methods of measurement frequently have R^2  $>0.16$ .

With 42 participants in each group, power is limited for the tests to examine differences in error between PortionSize™ and MyFitnessPal; therefore, these comparisons are exploratory.

The reliability of each apps' food intake estimates will be quantified with intraclass correlation coefficients (ICCs), and reliability will be supported if the ICC is significant and  $\geq 0.50$ . A power analysis indicates that, with 2 observations per subject, an ICC of 0.54 can be detected with 23 subjects at 80% power. The power analysis was conducted in R software using the 'ICC.Sample.Size' package based on Zou. Regression-based exploratory analyses are powered to detect an R^2 of 0.127 and thus have ample power.

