## **Background**

Accurately quantifying food intake is vital to promoting health and reducing chronic disease risk. Food intake encompasses energy intake, nutrient intake (macronutrients, micronutrients, vitamins, minerals), and intake of various food groups (e.g., fruits, vegetables), and thus reflects the nutritional status of individuals. Nutrition affects disease risk, including risk of developing obesity, diabetes, and cancer, all of which negatively affect the United States (U.S). Nonetheless, accurate assessment of food and nutrient intake has remained challenging, despite an improvement in methods. Self-report methods, namely food records, are a mainstay of nutritional epidemiology research, with food recall being another popular method. These methods rely on the participant to accurately estimate portion size and, for food recall, remember what was consumed. The accuracy of these methods have been questioned and the problems with human recall have been comprehensively outlined. As a result, there remains a significant need for methods that are sufficiently accurate to provide researchers with good outcome data and to guide health promotion efforts.

The PortionSize™ app was designed by our laboratory to overcome the limitations outlined above, and to guide users to follow specific diets. PortionSize™ relies on users capturing images of their food selection and waste. Food intake data are immediately provided since the user relies on built in tools, including templates, to estimate portion size. However, despite promising early indications, the PortionSize™ app has yet to be validated. Determining the accuracy and reliability of PortionSize™ is vital before the app can be used by people to obtain immediate feedback about their food intake. We accordingly aim to test the reliability and validity of PortionSize™ in a semi-controlled free-living environment using food provision. We will also test the reliability and validity of the MyFitnessPal app in a semi-controlled free-living environment. The accuracy of the apps will also be compared to each other.

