### ***Day 1***

Participants will return to the lab before breakfast in the morning to be weighed (non-metabolic) and be provided with the first cooler of food to consume for the remainder of the day. The coolers will contain about 1.3 times the participant's overall estimated energy needs, with ~20%, 30%, 40%, and 10% of energy provided as breakfast, lunch, dinner, and snacks, respectively. Staff will attempt to provide a day's worth of food that reflects 50% carbohydrate, 20% protein, and 30% fat (+/- 5%). The Mifflin St. Jeor Equation will be used to calculate basal metabolic rate (BMR), and total energy requirements will be calculated by multiplying BMR by an activity factor of 1.5. This value then will be multiplied by 1.3 to provide 30% more energy than the person requires. Participants will be instructed to only consume foods and beverages (with the

exception of water and non-caloric beverages such as black coffee or plain tea) from the cooler, but they can eat/drink as much or as little as they wish. Participants who report drinking diet, regular sodas, or sweet teas will be provided with their preferred beverage in their cooler, and efforts will be made to provide these beverages in typical store-bought containers (e.g., 12-ounce cans). All food and beverage items will be pre-weighed and weighed immediately upon return per our previous methods. We may include dietary supplement(s) on certain days, though the supplement may vary among participants (e.g., multivitamin, energy bar or shake, etc.).

This visit will last approximately 15-30 minutes.

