### **Day 2**

Participants will return to the lab before breakfast in the morning to be weighed (non-metabolic) and to return their cooler from Day 1. They will then pick up a new cooler containing their food and beverages for Day 2. The cooler content and procedures are the same as described above though the menus of foods in the cooler may differ each day. This visit will last approximately 15-30 minutes.

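### The ICC ≥ 0.50 rule for app reliability is confounded with how people eat from day to day and how much they differ from one another, and the observations and ICC form are not defined

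*Combined protocol and SAP*

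**What the plan says.** Reliability is a stated aim. The Background says: "We accordingly aim to test the reliability and validity of PortionSize™ in a semi-controlled free-living environment using food provision", and sets the same aim for MyFitnessPal.

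The only test of that aim is in Power calculation: "The reliability of each apps' food intake estimates will be quantified with intraclass correlation coefficients (ICCs), and reliability will be supported if the ICC is" (two conditions follow: statistical significance and a value of at least 0.50). The sample-size statement is that "with 2 observations per subject, an ICC of 0.54 can be detected with 23 subjects at 80% power". The section does not say what the two observations are, whether the ICC is one-way or two-way, or whether it refers to a single day or an average of days. Weighed intake does not enter the rule.

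Other sections fix which repeats exist:

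- Study Design gives each app one three-day period, and Baseline (and Day 0) leaves the run-in day out of the analysed days.
- Day 1 lets participants eat as much or as little of the cooler as they like, and sizes it to the person: "The coolers will contain about 1.3 times the participant's overall estimated energy needs".
- Day 2 adds that "the menus of foods in the cooler may differ each day", and Day 3 says much the same.
- No visit has the same food estimated twice with the same app.

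Outcome measures already defines error as the app value minus the weighed value, for other analyses.

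**The concern.** A reliability coefficient should separate instrument noise from real differences in what is measured. Here the only repeats of one app within a person are different days of eating. If the ICC is taken over those days, real change in intake counts as if it were unreliability, and real differences between people count as if they were reliability. The second effect is partly built in, because coolers are scaled to energy need and recruitment is stratified by sex and BMI.

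At stake is the answer to half of the stated aim. Followed as written, the rule can withhold support from an app that records every day correctly, or give opposite answers for the same app in samples that eat differently. Weighed intake on the same days would separate these effects but is not used for this purpose.

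**Working it through.** **1. The plan's own figure.** Inputs from Power calculation: k = 2 observations, ICC ρ = 0.54, power 80%. The section gives 0.05 for the equivalence test ("energy (kcal) intake as the outcome variable, alpha = 0.05") but no alpha for the ICC. I assume 0.05 two-sided and a null of zero.

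N = 1 + 2k(z_α + z_β)² / [(k − 1)(ln C₀)²], with C₀ = 1 / [1 + kρ/(1 − ρ)].

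C₀ = 1 / (1 + 2 × 0.54/0.46) = 0.2987 and ln C₀ = −1.2083. So N = 1 + 4 × (1.960 + 0.842)² / 1.460 = 22.5, which rounds up to 23. The stated 23 is reproduced. The match implies a null of zero, so a significant result shows only that the ICC differs from zero. At 42 subjects an observed ICC of about 0.30 (k = 2) or 0.18 (k = 3) is already significant, and the 0.50 cut-off therefore decides the outcome.

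**2. What the ICC contains.** For single-day app estimates with independent components:

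ICC = (B + S) / (B + S + D + E)

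B is between-person variance of true intake, S the variance of stable person-specific app bias, D true day-to-day variance within a person, and E day-level app error. For an error-free app S = E = 0, and the ICC is B/(B + D). This is below 0.50 whenever the day-to-day CV exceeds the between-person CV, whatever the mean.

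**3. How often an error-free app falls short.** The documents give neither B nor D. I take between-person CV 20% and vary the day-to-day CV. As a plausibility check, estimated energy need (Mifflin-St Jeor × 1.5), over the eligible ages and sexes with assumed heights, has a between-person CV of about 18% with BMI up to 40 and 21% with BMI up to 50.

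For 42 people and 3 days, F = MSB/MSW is distributed as [(1 + 2ρ)/(1 − ρ)] times an F variable on 41 and 84 degrees of freedom. The single-day ICC is below 0.50 when F < (1 + 2 × 0.5)/(1 − 0.5) = 4. The average-measures ICC, 1 − 1/F, is below 0.50 when F < 2.

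| Day-to-day CV | True single-day ICC | P(single-day ICC < 0.50) | P(3-day average ICC < 0.50) |
|---|---|---|---|
| 10% | 0.80 | 0% | 0% |
| 15% | 0.64 | 5% | 0% |
| 20% | 0.50 | 51% | 1% |
| 25% | 0.39 | 89% | 9% |
| 30% | 0.31 | 98% | 30% |

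Example at 25%: ρ = 0.04/(0.04 + 0.0625) = 0.39, the multiplier is 1.78/0.61 = 2.92, and P(F₄₁,₈₄ < 4/2.92) = 0.89. With k = 2 the single-day figure there is 81%. With between-person CV 30% and three days, the single-day failure rates are 0%, 0%, 1%, 16% and 51%.

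**4. App error does register.** At the plan's mean of 2,360 kcal, between-person CV 20% (SD 472) and day-to-day CV 10% (SD 236), day-level error SD of 0, 200, 400 and 600 kcal gives ICC 0.80, 0.70, 0.51 and 0.35.

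**5. The same app in different samples.** Hold error SD at 400 kcal and day-to-day CV at 10%, so D + E = 236² + 400² = 215,696. Between-person CV 15%, 20% and 30% (SD 354, 472, 708) gives 125,316/341,012 = 0.37, 222,784/438,480 = 0.51 and 501,264/716,960 = 0.70. The app has not changed, but its position relative to 0.50 has.

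**The case against.** **The food-day reading is inferred.** The plan never says that the ICC runs over days, and its two observations do not match three analysed days. Pairing the app value with the weighed value is not excluded, and on that pairing an error-free app scores 1.0. This stands as a limit on certainty. But such a pair measures agreement, which the equivalence tests and Bland-Altman analysis already cover, and it fits the wording about the reliability of each app's estimates less well. On either reading the observations need defining.

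**The failure rates depend on the ICC form and on assumed variances.** This stands. At 25% against 20%, moving from a single-day to a three-day average ICC takes the failure rate from 89% to 9%. With low day-to-day variation an error-free app passes almost always.

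**A reader might infer that the ICC says nothing about the app.** The documents do not support that: step 4 shows that day-level error lowers it materially. The measure is confounded, not uninformative.

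**A reader might also infer that a grossly wrong app could be endorsed.** An app recording exactly half of each day's intake has the same ICC as a perfect one, and a user who logs the whole cooler would look very consistent. These are failures of validity. A 50% shortfall lies far outside the ±17.9% bound. If usual intake is assumed to be 90% of need, logging a cooler at 130% of need overstates intake by 1.3/0.9 − 1 = 44%. The equivalence tests are there to catch both.

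**Conclusion.** The concern holds in a limited form. The observations and ICC form are undefined, and on the most natural reading a fixed 0.50 cut-off on raw intake cannot be interpreted as app reliability. The direction follows from algebra: a single-day ICC for an error-free app has a true value below 0.50 whenever day-to-day CV exceeds between-person CV. The size does not follow from the documents. For an error-free app with between-person CV 20%, 42 people and three days, failure runs from about 0% to 98% as day-to-day CV goes from 10% to 30%, and from 0% to 30% with an average-measures ICC.

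The stated 23 subjects is correct for the null of zero that it implies, and the primary equivalence analyses do not depend on this rule. The change should be made because reliability is a stated aim and this is its only specified test. Confidence is moderate, since the food-day reading is inferred and the variances are assumed.

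**What to change.** In Power calculation, and in Outcome measures where the analyses are listed:

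1. State that the observations are Days 1 to 3 of each period, and name the ICC form (one-way or two-way, single-day or average). Align the two-observation sample-size statement with that choice.
2. Compute the same ICC for weighed intake on the same participant-days. Report the app's ICC against it, as a difference or ratio with a bootstrap confidence interval.
3. Base the reliability statement for each app on the within-person, day-to-day SD of error, using the definition of error already in Outcome measures.
4. Draw no reliability conclusion from a raw ICC of at least 0.50 alone. If it is still reported, label it as day-to-day consistency of reported intake.

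The cost is analysis text only, because weighed intake is already collected for every cooler day. The price is the loss of a simple pass/fail cut-off.

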## Methods

### Study Design

We will recruit adults to use the PortionSize™ app and the MyFitnessPal apps in free-living conditions, where participants will consume pre-weighed food from a cooler, which provides a test of nutrient intake in free-living conditions. Participants will consume pre-prepared and pre-weighed foods from a cooler for two non-consecutive three-day periods that are separated by approximately one week. In a within subjects and randomized, counterbalanced design, participants will use PortionSize™ during one three-day period and MyFitnessPal during the other period. Following our previous methods, participants will pick up a cooler in the morning and, at approximately the same time, return the cooler from the previous day, allowing us to weigh food waste (i.e., determine food intake since the foods were weighed when they were put in the cooler). This procedure allows us to test the accuracy of the apps at measuring energy and nutrient intake in free-living conditions. Participants will be trained in our clinic/laboratory to use the apps following the procedures of Study 1.

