### ***Baseline (and Day 0)***

Participants will attend an in-person visit at Pennington for Baseline, which occurs during Period 1, to be randomized and trained how to use the app that they will use first. During Day 0, which occurs during Period 2, participants will be trained to use the app that they will use second. These visits will last ~45 to 60 minutes. The training will teach participants how to report food intake and estimate portion size per our standard procedures. Participants will receive training by study staff members on the app that they will use for that period. That is, individuals randomized to use PortionSize™ first will be trained on PortionSize™, whereas those randomized to use MyFitnessPal first will be trained on MyFitnessPal. This first day is usually a partial day of data collection and will serve as a run-in/familiarization period for the participants, during which they will be instructed to use the app for the remainder of the day. These data will not be analyzed as part of the 3-day use period.

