### **Day 3**

Participants will return to the lab before breakfast in the morning to be weighed (non-metabolic) to return their cooler from Day 2. They will then pick up a new cooler containing their food and beverages for Day 3. The cooler content and procedures are the same as described above though the menus or foods in the cooler may differ each day. This visit will last approximately 15-30 minutes.

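### The 80% power quoted for reliability reproduces only for a test of ICC = 0; it does not cover the 0.50 cut-off that decides the rule, nor the three analysed days per app

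*Combined protocol and SAP*

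**What the plan says.** The Power calculation section gives the reliability criterion: each app's "food intake estimates will be quantified with intraclass correlation coefficients (ICCs), and reliability will be supported if the ICC is significant and" at least 0.50. It then states that "with 2 observations per subject, an ICC of 0.54 can be detected with 23 subjects at 80% power". It does not give the null value, the sidedness, the ICC model, whether 0.50 applies to the estimate or to a confidence limit, or what the 2 observations are. The Outcome measures section does not mention the ICC.

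On the data available for it:

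- Study Design: participants use PortionSize "during one three-day period and MyFitnessPal during the other period". Each app therefore has one period.
- Baseline (and Day 0): the training day is a run-in, and "These data will not be analyzed as part of the 3-day use period". That leaves Days 1 to 3, three analysed days per app.
- Day 1: participants eat from the cooler, but "they can eat/drink as much or as little as they wish". Day 3: "the menus or foods in the cooler may differ each day".

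Reliability is a stated aim for both apps. The Background says so for PortionSize and adds: "We will also test the reliability and validity of the MyFitnessPal app in a semi-controlled free-living environment".

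**The concern.** The rule has two parts, significance and a value of at least 0.50. The 80% figure follows it directly without saying which part it covers. If it covers only significance, the plan gives no probability of meeting the criterion it will report. The 2 observations cannot be two periods with the same app, and they are not the three analysed days.

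Two things are at stake. Whether an app is called reliable could depend on an ICC form, or on a reading of the 0.50, chosen after the data are seen. And if days are the replicates, a low ICC could be blamed on the app when it reflects real differences in eating from day to day.

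**Working it through.** **Inputs.** From the Power calculation section: k = 2 observations, ICC 0.54, 23 subjects, 80% power, 42 analysable participants, cut-off 0.50. Alpha 0.05 is stated there for the equivalence test and is assumed to apply here. From Study Design and Baseline (and Day 0): k = 3 analysed days per app. The calculations assume a one-way random-effects model with normal data.

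**Step 1: reproduce the plan's 23.** With C = 1 + kρ/(1 − ρ), a test of ICC = 0 needs

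n = 1 + 2k(z_α + z_β)² / [(k − 1)(ln C)²].

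For k = 2 and ρ = 0.54, C = 1 + 2 × 1.174 = 3.348 and (ln C)² = 1.460. Two-sided 0.05 and 80% power give (1.960 + 0.842)² = 7.849. Then n = 1 + 4 × 7.849/1.460 = 22.5, so 23. The exact F test at n = 23 has power 0.802.

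Other settings do not give 23:

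- one-sided 0.05 with null 0: 17.9;
- two-sided with null 0.50: about 2,610;
- k = 3 with null 0: 11.3, so 12.

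The figure is therefore right for a two-sided test of ICC = 0 with 2 observations.

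**Step 2: which half of the rule binds.** The ANOVA ratio satisfies F/C ~ F(n − 1, n(k − 1)), and the single-measure estimate is (F − 1)/(F + k − 1). Significance against 0 (upper 0.025 point) needs:

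| n, k | critical F | as single-measure ICC |
|---|---|---|
| 23, 2 | 2.33 | 0.40 |
| 42, 2 | 1.85 | 0.30 |
| 42, 3 | 1.66 | 0.18 |

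An estimate of at least 0.50 needs F ≥ 1 + k, that is 3 or 4. This exceeds the critical value in every row, so the cut-off alone decides the outcome.

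**Step 3: probability of meeting the full rule, with 0.50 applied to the single-measure point estimate.** At a true ICC of 0.54:

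| n, k | test of ICC = 0 | significant and ≥ 0.50 |
|---|---|---|
| 23, 2 | 0.80 | 0.60 |
| 42, 2 | 0.97 | 0.64 |
| 42, 3 | >0.99 | 0.66 |

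For the last row, C = 1 + 3 × 1.174 = 4.522, and P(F(41, 84) ≥ 4/4.522) = 0.66. For the same design the probability is 0.49 at a true ICC of 0.50, 0.81 at 0.58, 0.87 at 0.60 and 0.96 at 0.65.

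**Step 4: other readings at n = 42, k = 3.**

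- Average-of-3-days ICC: an estimate of at least 0.50 means F ≥ 2. A true average ICC of 0.54 is a single-measure ICC of 0.54/(3 − 2 × 0.54) = 0.281. The test of 0 then has power 0.83, and the full rule is met with probability 0.61.
- 0.50 applied to the lower 95% limit of the single-measure ICC: F must exceed 4 × 1.664 = 6.66, which has probability about 0.07 at a true ICC of 0.54.
- The single and average forms disagree when 2 ≤ F < 4, that is for single-measure estimates from 0.25 to 0.50. At a true single-measure ICC of 0.54 this has probability 0.34.

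**Step 5: an error-free app, if days are the replicates.** With between-person SD s_b and day-to-day SD s_w in true intake, the single-measure ICC is s_b²/(s_b² + s_w²). It is below 0.50 whenever s_w > s_b. For the average of 3 days the ICC is s_b²/(s_b² + s_w²/3), below 0.50 only when s_w > 1.73 s_b. The documents give neither SD, so the size of this effect cannot be computed.

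**The case against.** The plan says only that an ICC of 0.54 can be detected. It does not promise an 80% chance of meeting the full rule, and 23 is correct for what it appears to cover. The value 0.54 is a detectable ICC, not an expected one. Any true value 0.04 above a cut-off will pass not far above half the time, and pass rates are 0.87 at 0.60 and 0.96 at 0.65. All of this stands. It means that the figure needs a label and a companion, not that it is wrong.

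Using 2 observations where 3 are available costs no power for the test of 0: with k = 3 the same test needs 12 subjects, and 42 are planned. That also stands. The mismatch is one of definition.

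The point about day-to-day eating depends on days being the replicates, which no section says. Recruitment across both sexes and a BMI range of 18.5 to 50 suggests a wide between-person spread, which would raise the ICC. This limits the point to a conditional one.

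A reader might infer that the power calculation is mistaken, that the study is too small, or that accurate apps will fail. The documents support none of these. The arithmetic reproduces, no expected ICC is stated against which the sample could be judged too small, and neither SD is given.

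**Conclusion.** The point holds as a gap in what the power figure covers. The quoted 80% belongs to a two-sided test of ICC = 0 with 2 observations, a null inferred because, of the settings tried, only it reproduces 23. The criterion to be reported also requires 0.50, and that part decides it. For 42 participants and 3 days, at a true value of 0.54, the probability of meeting the rule is 0.66 (single-measure point estimate), 0.61 (average of 3 days, with 0.54 on the average scale) or about 0.07 (lower 95% limit, single-measure). The spread shows how much depends on choices not yet fixed. The figures assume a one-way normal model and two-sided 0.05.

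Reliability is a stated aim but not a primary analysis, and neither the equivalence tests nor the sample size depends on it. The weight is minor to moderate.

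**What to change.** 1. Label the 23-subject figure as being for a two-sided test of ICC = 0 with 2 observations, and add the figure for the full rule and the actual design. Example wording: with 42 participants and 3 days per app, a one-way single-measure ICC that is significant against 0 (two-sided 0.05) and has a point estimate of at least 0.50 has probability 0.66 if the true ICC is 0.54, 0.81 if it is 0.58 and 0.87 if it is 0.60. If the average-of-3-days ICC is meant, give 0.61 at a true average ICC of 0.54. If 0.50 applies to the lower 95% limit of the single-measure ICC, give about 0.07 at 0.54.
2. In the same sentence, and before analysis, fix what the observations are, which ICC form is used and what the 0.50 applies to. The choice is the investigators'.
3. If days are the replicates, report beside each app's ICC the same ICC on weighed intake for the same participants and days. A low app value can then be compared with the value that true eating produced.

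The cost is two or three sentences and one extra ICC per app on weighed data already collected, with no added visits. The downside is that the stated probability becomes less favourable and the ICC form can no longer be chosen after the data are seen.

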### Outcome measures

The **primary analyses** assessing equivalence between PortionSize™ and the criterion measure (and MyFitnessPal and the criterion measures) will rely on equivalence testing using the Two One-side T-test (TOST) method. The null hypothesis of an equivalence tests is that the means are nonequivalent, i.e., the confidence interval of the mean of the test condition exceeds the pre-specified error bound. The alternative hypothesis is that the means are equivalent, and the mean difference between the experimental method and gold standard is hypothesized to be zero. Differences in error from PortionSize™ compared to error from MyFitnessPal will be assessed using dependent samples t-tests, with error calculated as the difference between each experimental method and the criterion variable (e.g., energy intake values from PortionSize™ minus energy intake values from weighed foods). These procedures will also produce results indicating if the error from each method differs from zero.

Subsequent regression-based **exploratory analyses** will determine if error from the apps varies by body mass (kg, BMI), age, or sex; and will evaluate differences in user satisfaction between the apps. Bland-Altman analysis will be used to test for differences in error variance over levels of the variable being measured (e.g., food intake).

Endpoints will be:

- Energy intake (kcal)
- User satisfaction and usability of the apps
- Nutrients (e.g., fat, carbohydrate, and protein as grams and percent energy from each macronutrient) and food groups (PortionSize™ only since it has the ability to provide output in food groups due to the link with the FNDDS database).

Other exploratory endpoints include human rater analysis of captured food images and the modified Dietary History Questionnaire III (DHQIII) as comparators for food and possible dietary supplement intake.

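### The exploratory regressions are called amply powered at R² 0.127, but on the basis that reproduces the plan's own R² 0.17 figure their power is about 67%

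*Combined protocol and SAP*

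**What the plan says.** All the power statements are in the Power calculation section of the combined protocol and SAP.

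- **Sample size.** "We expect no more than ~8% drop-out and will recruit at least 45 participants", and so "power analyses were conducted with a sample size of at least 42".
- **Alpha.** A level is given once, for the equivalence (TOST) calculation: "42 participants, energy (kcal) intake as the outcome variable, alpha = 0.05". Neither regression statement repeats it.
- **First regression figure.** For the Bland-Altman regression, "with at least 42 participants completing the PortionSize and MyFitnessPal condition", the plan says "we have 0.80 power to detect an R 2 of 0.17".
- **Second regression figure.** For the exploratory regressions, "Regression-based exploratory analyses are powered to detect an R 2 of 0.127 and thus have ample power". Apart from the general sample size that opens the section, nothing says how 0.127 was obtained.

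The Outcome measures section says what the exploratory regressions are for: to see whether "error from the apps varies by body mass (kg, BMI), age, or sex; and will evaluate differences in user satisfaction between the apps". It does not say whether these factors are tested one at a time or together.

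**The concern.** With the same people and the same kind of test, power falls as the R² to be detected gets smaller. A sample that reaches about 0.80 at R² 0.17 cannot also reach 0.80 at R² 0.127. So either the two figures rest on different bases, one of which is not given, or the second is wrong.

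This is the plan's only power statement for the question whether app error depends on body mass, age or sex. Recruitment is stratified by sex and BMI, so readers will look at these results. A plan that claims ample power invites a non-significant result to be read as showing that accuracy is the same across body size, age and sex. If power is well below 0.80, that reading is not available.

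**Working it through.** **Inputs**

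- n = 42 completers, and 45 as the upper case with no drop-out (Power calculation).
- R² = 0.17 with stated power 0.80, and R² = 0.127 with no stated power (Power calculation).
- Alpha 0.05, stated for the TOST only. Two-sided testing and one predictor are assumptions, checked in step 1.

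**Method.** F test of R² in linear regression: f² = R²/(1 − R²), noncentrality λ = n·f², degrees of freedom 1 and n − 2, power from the noncentral F distribution.

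**Step 1: reproduce the plan's R² 0.17 figure**

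- f² = 0.17/0.83 = 0.2048
- λ = 42 × 0.2048 = 8.60
- Critical F(1, 40) at 0.05 = 4.085
- Power = 0.816. The R² that has exactly 0.80 power is 0.164.

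This agrees with the stated 0.80 to within two points. With two predictors tested jointly, power at R² 0.17 would be only 0.715, so one predictor is the basis that fits.

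**Step 2: apply the same basis to R² 0.127**

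- f² = 0.127/0.873 = 0.1455
- λ = 42 × 0.1455 = 6.11
- Power = 0.674, so the chance of missing the effect is 1 − 0.674 = 0.326.
- With n = 45: λ = 6.55, power = 0.706.

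**Step 3: sample size for 0.80 power at R² 0.127**

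- n = 55 gives 0.793 and n = 56 gives 0.800.
- At 8% drop-out, 56/0.92 = 60.9, or about 61 recruits.

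**Step 4: sensitivity to the method and the model**

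| Basis | Power at R² 0.127 | Power at R² 0.17 |
|---|---|---|
| n = 42, one predictor, two-sided (steps 1 and 2) | 0.674 | 0.816 |
| Same, λ = (n − 2)·f² | 0.653 | 0.798 |
| Same, Fisher z | 0.643 | 0.782 |
| Same, simulated random normal predictor | 0.654 | 0.792 |
| n = 42, one factor (partial R²) in a 4-predictor model | 0.673 | 0.815 |
| n = 42, joint test of 2 / 3 / 4 predictors | 0.56 / 0.48 / 0.43 | 0.72 / 0.64 / 0.58 |
| n = 42, one predictor, one-sided 0.05 | 0.784 | 0.892 |
| n = 45, one predictor, one-sided 0.05 | 0.809 | 0.910 |
| 84 records treated as independent, 1 / 3 / 4 predictors | 0.93 / 0.83 / 0.78 | 0.98 / 0.94 / 0.92 |

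Every two-sided single-factor calculation with 42 people gives 0.64 to 0.67 at R² 0.127. The rows that bring 0.127 near or above 0.80 all put R² 0.17 at 0.89 or more, away from the 0.80 the plan states for it.

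**The case against.** The best reply is that this is a gap in reporting and not a proven miscalculation. The sentence states no power level, alpha or number of predictors, and the plan never says that its two regression figures share a basis. The basis used here is itself inferred, since the R² 0.17 sentence gives neither sidedness nor predictor count.

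Other origins for 0.127 are possible. A one-sided test at 0.05 reaches 0.80 with 44 people, inside the plan's range of 42 to 45. If both app records from each person are pooled in a four-predictor model, the R² detectable with 0.80 power is 0.131 for 84 records and 0.123 for 90, which brackets 0.127. The analyses are also labelled exploratory, no design decision depends on the figure, and the plan nowhere says that a null result will be read as absence of effect.

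Part of this stands. The source of 0.127 is unknown, the 67% is conditional, and the consequence is limited. But the alternatives do not support the sentence. None is documented. Asking whether error varies with a factor states no direction, so one-sided testing does not follow from the aim. Pooling treats two records from one person as independent, although the design is within-person and body mass, age and sex are characteristics of the person.

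**Conclusion.** The concern holds. With 42 completers, a single factor and two-sided alpha 0.05, which is the basis that reproduces the plan's R² 0.17 figure, power at R² 0.127 is about 67% (64% to 67% by method). It is 71% if nobody drops out. The trial would need 56 completers, 14 more than the 42 it plans on, to reach 0.80. A joint test of several factors would have less power still.

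The conclusion rests on that inferred basis. It does not show how 0.127 arose. It does show that the documented design does not support the claim of ample power. Only exploratory analyses are affected; the TOST, its bounds and the sample size are untouched.

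**What to change.** Delete the claim of ample power and replace the sentence with wording such as:

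> *42 completers give 0.80 power to detect an R² of about 0.16 to 0.17 for a single factor (two-sided alpha 0.05), and about 67% power at R² 0.127. Non-significant moderator results in these exploratory analyses are not evidence of no effect.*

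If 0.127 came from another calculation, state its number of people or records, alpha, sidedness, target power and number of predictors. If records from both apps were pooled, say how the pairing within a person was handled.

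It would also help to state separately the basis for the user-satisfaction comparison, where each person contributes two records; that is missing detail and not an error.

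The cost is one or two sentences in the protocol and a less favourable stated figure. The sample size, primary analysis and conduct do not change.
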